Lower extremity compression wraps are a low cost inpatient intervention when managing fluid overload in patients hospitalized for acute systolic heart failure, and presenting with lower extremity edema. Also, compression stockings are mainstay devices in the outpatient setting for improving symptoms of lower extremity edema in chronic systolic heart failure. However, the utility of compression wraps in managing patients hospitalized for acute systolic heart failure, and transitioning to the use of compression stockings for symptom management upon discharge, has not been thoroughly assessed. Current practice suggests use of lower extremity compression wraps can facilitate intravenous diuresis while inpatient, achieve more optimal discharge dry weight, and lower BNP levels prior to discharge. Demonstrating efficacy of such a low-cost, low-risk intervention in decreasing hospital stay and achieving more favorable patient outcomes will have considerable impact on standard practice.

• SUBJECT POPULATION AND ELIGIBILITY

Inclusion criteria: patients age greater than 18 and less than 85 years of age, admitted to I5 with Acute Systolic Heart Failure, and an ejection fraction of less than 50% as determined by echocardiogram within 6 months, requiring inpatient management with intravenous diuretic therapy. Must have a diagnosis of acute systolic heart failure (by ICD coding) on admission, of any underlying etiology. Must have documentation of pitting edema on primary assessment.

Exclusion criteria: patients who do not meet inclusion criteria, who cannot tolerate IV diuresis, who cannot wear or tolerate lower extremity compression stockings or wraps; active diagnosis of ESRD on dialysis or peripheral neuropathy; ejection fraction greater than 50% as evaluated by echocardiogram within 6 months.

Control population: Patients meeting inclusion criteria, managed on I5 for acute systolic heart failure with standard medical therapy without the use of lower extremity compression wraps.

This will allow direct comparison of the effect of intervention (lower extremity compression wraps) on the previously listed endpoints on the same patient population.

Since this study evaluates an already established component of standard medical practice, there will be no discrimination of patient populations in enrollment outside of the inclusion and exclusion criteria.

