Patients will be enrolled exclusively based on inclusion and exclusion criteria, undergoing randomization into intervention or control groups. No screening tools will be used.

• STUDY PROCEDURES

The study will be an internally funded, parallel-intervention clinical trial studying the use of lower extremity compression stockings as adjuvant therapy to standard medical care in management of patients admitted for acute systolic heart failure. There will be two arms, intervention and control. 120 patients will be enrolled in the study, 60 to each arm, to achieve power above 80% with an alpha of 0.05, measuring continuous primary endpoints of average percent reduction in weight after diuresis, average change in BNP from admission to discharge, and average length of admission in days.

Data will be collected by Henry Ford personnel, for 120 patients previously admitted after January 2018 and managed on the HF Main cardiology I5 floor meeting inclusion criteria and managed with standard medical therapy without the use of compression stockings, and will undergo review by research team for enrollment into the control group. If additional patients are needed to achieve enrollment number of 60 control subjects, patients will be enrolled and randomized prospectively by the research team. Data collected retrospectively will be performed through Epic health medical record and charted on Excel spreadsheet, and will include admission length of stay, daily weights, daily urine outputs, daily diuretic dose and type(s) used, admission BNP, and discharge BNP. Research team will also perform chart review on enrolled patients to evaluate for 30-day readmission rate.

The intervention arm will include patients enrolled and randomized by the research team meeting inclusion criteria, and managed on HF Main cardiology I5 floor. This population will receive bilateral lower extremity compression wraps (ACE bandages) on day 1 of admission in addition to standard medical therapy. Data will be collected by the research team through Epic health medical record and will be charted on Excel spreadsheet, and will include admission length of stay, daily weights, daily urine outputs, daily diuretic dose and type(s) used, admission BNP, and discharge BNP. These charts will also undergo review by research team to evaluate for 30-day readmission rate.

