Anticipated benefits include: decreased length of stay, decreased amount of diuretic used, increased percentage of weight achieved through diuresis; greater percent of BNP reduction; decreased 30-day readmission rate.

- **RENUMERATION/COMPENSATION**

No compensation offered

- **COSTS**

There is no additional cost anticipated for this study outside of standard medical management of acute systolic heart failure and any additional medical conditions treated during the hospital admission.

- **ALTERNATIVES**

Intervention does not involve offering an established efficacious therapy to patients, and conversely control group is not being withheld from any known therapy that affects morbidity/mortality. No known alternatives.

- **CONSENT PROCESS AND DOCUMENTATION**

Co-investigators and sub-investigators enrolling patients will be responsible for obtaining consent from patients prior to enrollment. This will involve presentation of consent document with description of study. Patients will have the opportunity to privately ask questions and receive answers at the time of enrollment after the study is described to them in detail, including risks and benefits. There will be no duress or undue influence, as intervention is already a standard of medical practice. Patients will have the opportunity to refuse intervention. Patients will not be enrolled if they have diminished capacity or learning disability, or impairment of any kind. If patient is non-English speaking, consent form will be translated using standard translator services (in person translator, translator phone). Consent documentation will be stored on the Henry Ford secured OneDrive Microsoft cloud server. This information will only be accessible by research team. Information will be stored for the entirety of the study, and promptly discarded in accordance with HFHS regulation at the completion of the study tentatively scheduled for January 2020. Information collected on patients excluded from the study will be discarded at the time of exclusion in accordance with HFHS regulation.

- **WITHDRAWAL OF SUBJECTS**

Patients withdrawn from study will be notified, and information gathered from enrollment period will be analyzed as intention to treat. All information will be destroyed appropriately at the time of withdrawal.

- **PRIVACY AND CONFIDENTIALITY**

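### The consent section adds an undefined capacity and impairment exclusion that is missing from the eligibility criteria and not stated to apply to the chart controls, so the arms may differ in case mix

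*Combined protocol and SAP*

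**What the plan says.** Three parts of the combined protocol and SAP bear on who may enter.

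- **Subject Population and Eligibility.** Besides failure to meet the inclusion criteria and inability to tolerate IV diuresis or compression, the exclusions are "active diagnosis of ESRD on dialysis or peripheral neuropathy; ejection fraction greater than 50% as evaluated by echocardiogram within 6 months". Capacity, learning disability and general impairment are not mentioned. The section describes the control population and then claims: "This will allow direct comparison of the effect of intervention (lower extremity compression wraps) on the previously listed endpoints on the same patient population". It closes with: "Patients will be enrolled exclusively based on inclusion and exclusion criteria, undergoing randomization into intervention or control groups".
- **Study Procedures.** Controls are sought first from records: data will be collected "for 120 patients previously admitted after January 2018 and managed on the HF Main cardiology I5 floor meeting inclusion criteria", without compression, and these patients "will undergo review by research team for enrollment into the control group". The criteria of that review are not given. Prospective, randomised controls are added only if the charts do not yield 60. Wrap patients are all enrolled prospectively. The retrospective data items are length of stay, weights, urine output, diuretics and BNP; no capacity or impairment item is among them.
- **Consent Process and Documentation.** Within the description of how consent is obtained, a further rule appears: "Patients will not be enrolled if they have diminished capacity or learning disability, or impairment of any kind". Impairment is not defined.

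The analysis, also under Study Procedures, consists of descriptive statistics, univariate comparisons, t-tests and ANOVA. No matching or covariate adjustment is planned.

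**The concern.** An eligibility rule that sits only in the consent procedure naturally acts on patients who go through that procedure. Wrap patients do. Chart controls are not described as doing so, and their stated filters contain no equivalent. A past patient with documented dementia could pass the stated chart filters, while the same patient admitted today would be refused entry to the wrap arm.

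This can be separated from the general weakness of comparing past records with prospective patients. Even if the chart patients were alike in period and care, this rule could still select the two arms differently. If barred patients differ in length of stay for reasons unrelated to fluid removal, an unadjusted t-test would attribute that difference to the wraps. Because impairment is not recorded for the chart patients, the imbalance could not be measured afterwards. The loose wording is a second problem: two enrolling investigators could apply it differently.

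**Working it through.** **Step 1. Compare the rules as written.**

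| Group | Meets inclusion criteria | Listed exclusions | Capacity/impairment rule |
|---|---|---|---|
| Wrap arm (prospective) | Yes | Yes | Yes, at consent |
| Prospective top-up controls, if any | Yes | Yes | Yes, at consent |
| Chart controls | Yes | Not stated separately | Not stated |

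The listed criteria cannot be the exclusive basis for enrolment while the consent section adds another. That contradiction needs no assumption. One-sided application is the natural consequence of where the rule sits, but it is not stated.

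**Step 2. The plan's own figure.** The plan gives 60 per arm for power above 80% at alpha 0.05, with no expected difference or SD for any endpoint, so the figure cannot be reproduced. Solved backwards (two-sided), the detectable standardised difference is (1.960 + 0.842) × √(2/60) = 0.511 SD. The stated power can be neither confirmed nor refuted, and the SD of length of stay has to be assumed below.

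**Step 3. Size of a possible length-of-stay shift.** Let q be the share of chart controls whom the rule would have barred and D their mean excess stay in days. If all 60 controls are chart patients and the rule is not applied to them:

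shift = q × D

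Assumed ranges: q = 10–30%, D = 1–3 days, SD = 3, 4 or 5 days. None comes from the documents. The shift runs from 0.10 × 1 = 0.1 day to 0.30 × 3 = 0.9 day.

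**Step 4. Rejection rate when wraps have no effect.** Two-sided t-test at 0.05 with 60 per arm, df = 118, and noncentrality = (shift/SD) × √(60/2) = (shift/SD) × √30. For example, at SD 4 and a shift of 0.6 day, 0.15 × 5.477 = 0.822, which gives 12.9%.

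| Shift (days) | Example q × D | SD 3 | SD 4 | SD 5 |
|---|---|---|---|---|
| 0.1 | 10% × 1 | 5.4% | 5.2% | 5.1% |
| 0.2 | 10% × 2 | 6.5% | 5.9% | 5.5% |
| 0.4 | 20% × 2 | 11.2% | 8.4% | 7.2% |
| 0.6 | 20% × 3 | 19.2% | 12.9% | 10.0% |
| 0.9 | 30% × 3 | 37.1% | 23.1% | 16.5% |

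This treats the SD as equal in both arms. Mixing barred and non-barred patients widens the control variance to SD² + q(1 − q)D². A normal approximation with that variance lowers the last row to 34.6%, 22.4% and 16.2%, so the picture does not change.

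**Step 5. Sign and dilution.** If D = 0 the shift is zero. If D is negative the shift goes against wraps, with the same rejection rates in the other direction. Prospective controls shrink it in proportion: if half the controls were prospective, the 0.9-day shift would become 0.5 × 0.9 = 0.45 day, and the 23.1% at SD 4 would fall to about 9.4%.

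**The case against.** The strongest reply is that the documents never say the rule is withheld from charts. The consent section bars enrolment without naming an arm, and Study Procedures uses the word enrolment for chart controls too, after a review whose criteria are not given. The team may intend to apply it there. This stands: a reader might infer that the rule never touches chart controls, and the text does not support saying so. It supports only that no such step is stated. Since the review rule is unstated, the gap remains.

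Second, a reader might infer that length of stay is tilted toward wraps. Nothing in the documents links impairment to length of stay, or to readmission. The direction is an assumption, and the high rejection rates need the most extreme prevalence and the most extreme excess stay together. This also stands.

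Third, read literally, the impairment phrase would take in hearing, mobility or renal impairment. That reading is strained. The phrase follows diminished capacity and learning disability in a paragraph about consent, and the separate exclusions for dialysis-dependent renal disease and peripheral neuropathy would be largely redundant if it covered physical or organ impairment. The wording needs definition, but this reading should carry no weight in the bias argument.

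Fourth, this is one part of a larger problem: past chart patients are compared with people who agreed to take part. That is fair. It limits what the fix can achieve, but does not make the contradiction disappear.

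**Conclusion.** The point holds in a limited form. Certain from the text: an undefined exclusion appears only in the consent section, is absent from the eligibility list, and contradicts the statement that the list alone governs enrolment. Also certain: no matching filter is stated for chart controls, and no adjustment is planned. It follows that the arms may differ in case mix, and the claim that both come from one patient population is not secured.

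Whether length of stay is biased, by how much and in which direction cannot be determined from the documents. If barred patients stay longer, the bias favours wraps. Under the assumed inputs and with all controls from charts, the two-sided rejection rate under no effect runs from about 5% to about 37%, negligible at one end and serious at the other. The correction should be made because the contradiction is plain and cheap to remove, not because a material bias has been shown.

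**What to change.** 1. Move the exclusion into the list under Subject Population and Eligibility, and have the consent section refer to it.
2. Replace the general impairment phrase with a definition limited to capacity to consent, worded so that it can be applied from admission-day chart documentation: for example, documented dementia, delirium, lack of decision-making capacity or intellectual disability.
3. State that the research team's review applies this criterion to every chart control before acceptance, using admission-day documentation only, so that later events in the stay cannot influence selection.
4. Report how many patients the criterion removes in each arm.

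The cost is protocol wording and one extra item in the chart review. Some candidate control charts will drop out, but 120 are to be reviewed for 60 places. Charts record capacity less completely than a bedside consent discussion, so the match will be imperfect. Other differences between past chart patients and consented patients, such as willingness to take part, are not cured by this change.
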